2.4.2 Known Potential Benefits

The benefit of this study is the ability to obtain a lifesaving lung transplant rather than risk death while waiting on the list for a HCV negative organ. In addition, many of the donors with HCV infection have otherwise ideal donor characteristics for lung donation and our patients could benefit from access to better quality organs.

3 Objectives and Purpose

3.1 Primary Objective

This pilot feasibility study is being conducted to determine safety and efficacy of the strategy of transplantation of lungs from HCV positive donors (with or without evidence of active HCV viremia) into HCV-negative recipients on the NYU Langone Health lung transplant waiting list, with subsequent anti-HCV therapy to treat infection in the recipient.

3.2 Secondary Objectives (if applicable)

Secondary objectives will include characterization of the incidence of HCV viremia in recipients whose lung donors were HCV positive.

For those who develop viremia we will also characterize the time course of the development of viremia, and subsequent clearance of viremia after treatment.

CONFIDENTIAL

4 Study Design and Endpoints

4.1 Description of Study Design

This will be an open-label, single arm, single center trial of the use of HCV positive lung donors for HCV negative recipients, followed by treatment of HCV in recipients.

4.2 Study Endpoints

4.2.1 Primary Study Endpoints

The primary endpoint will be percentage of patients with sustained virologic response after treatment for HCV after lung transplant. This endpoint was chosen as primary because it will enable us to evaluate the safety of transient exposure to HCV at the time of lung transplantation. The expectation is that all patients who develop HCV viremia will achieve SVR (cure) following treatment with Mavyret.

4.2.2 Secondary Study Endpoints

Secondary endpoints will include:

1-year patient survival rates in HCV negative lung recipients who receive a lung transplant from a HCV positive donor.

Incidence of acute HCV viremia among HCV negative recipients who receive a lung transplant from a HCV positive donor.

These endpoints will enable us to assess the risks associated with this approach to lung transplantation and will allow us to better understand the risks of this approach to risks associated with remaining on the waiting list for a HCV-negative organ offer.

5 Study Enrollment and Withdrawal

5.1 Inclusion Criteria

In order to be eligible to participate in this study, an individual must meet all of the following criteria:

1. Listed for an isolated lung transplant at NYU Langone Health
2. Between 18-70 years of age
3. Able to travel to the NYU Langone Health for routine post-transplant visits and study visits for a minimum of 6 months after transplantation
4. No active illicit substance abuse
5. Weight at least 40kg
6. Women of childbearing potential must agree to use birth control in accordance with Mycophenolate Risk Evaluation and Mitigation Strategy (REMS) after transplant due to the increased risk of birth defects and/or miscarriage
7. Both men and women must agree to use at least one barrier method after transplant to prevent any secretion exchange
8. Able and willing to provide informed consent

Furthermore, the deceased donors from whom the organs will be procured must meet the following criteria:

1. Detectable HCV RNA Quantitative (PCR) or positive anti-HCV antibody
2. Donor lung meets standard NYU Langone Health clinical criteria for procurement

5.2 Exclusion Criteria

An individual who meets any of the following criteria will be excluded from participation in this study:

CONFIDENTIAL

1. HCV RNA positive or history of previously treated HCV
2. Evidence of active hepatitis B infection or on active antiviral treatment for HBV
3. Pregnant or nursing (lactating) women
4. Use of strong CYP3A inducers
5. Requires multi-organ transplant

Furthermore, the deceased donors from whom the organs will be procured will be excluded if they meet any of the following criteria:

1. Confirmed HIV positive
2. Confirmed HBV positive (positive hepatitis B surface antigen, and/or detectable Hepatitis B virus DNA)
3. Known previously failed treatment for HCV
4. Donor age >60 years

5.3 Vulnerable Subjects

Vulnerable subjects will not be eligible for enrollment.

5.4 Strategies for Recruitment and Retention

Recruitment of patients will occur during routine evaluation visits to determine candidacy for a lung transplant at NYU Langone Health. Patients will be informed of the option to enroll in this study, and if interested, detailed information pertaining to the risks and benefits of the trial will be provided.

The signing of the acknowledgment to consider participation in the study will occur in the outpatient clinic. No additional information about potential candidates will be collected to determine interest or candidacy for this trial than would otherwise be normally collected as per standard of care for evaluation for a lung transplant.

Written informed consent for actual enrollment in the study will occur in the inpatient setting once available organ offer has been identified and the patient is admitted for potential transplantation.

The target sample size will be 20 patients.

5.4.1 Use of Data Core/Epic Information for Recruitment Purposes

This study will utilize EPIC to identify subjects.

Any recruitment information sent by email will utilize Send Safe email.

Potential subjects will already be known to the study team, as they will be under their care as candidates and/or waitlist registrants for lung transplant. The study team will conduct an in person consultation with the patients to explain the study as well as discuss the risks, benefits, and alternatives

Approved recruitment language will be used to communicate the reason they are being contacted and subjects will be asked if they are interested in participating in this specific study. Should the potential subjects agree, the study team will provide the subjects with information regarding the next steps for participation.

If a subject requests information regarding opting out of further recruitment for all research, subjects will be directed to contact [contact] or [name].

CONFIDENTIAL

5.5 Duration of Study Participation

Duration of participation is expected to be 12 months minimum, which will be 10 months of follow up post therapy with Mavyret.

5.6 Total Number of Participants and Sites

Twenty patients are expected to be enrolled and transplanted. No sites outside of NYULMC will enroll patients.

5.7 Participant Withdrawal or Termination

5.7.1 Reasons for Withdrawal or Termination

Participants are free to withdraw from participation in the study at any time upon request. An investigator may terminate participation in the study if:

- Any clinical adverse event (AE), laboratory abnormality, or other medical condition or situation occurs such that continued participation in the study would not be in the best interest of the participant
- The participant meets an exclusion criterion (either newly developed or not previously recognized) that precludes further study participation

5.7.2 Handling of Participant Withdrawals or Termination

Discontinuation of the study agent is not anticipated, as this will place patients at risk to develop acute or chronic HCV. For patients who do elect to discontinue the study agent Mavyret due to intolerance or SAEs/AEs, the following steps will be taken:

- Hepatology consultation to guide management, which could include:
- Continued surveillance for evidence of HCV viremia in patients who had cleared their viremia
- Conversion to an alternate HCV treatment that can be tolerated by the patient

5.8 Premature Termination or Suspension of Study

This study may be temporarily suspended or prematurely terminated if there is sufficient reasonable cause. Written notification, documenting the reason for study suspension or termination, will be provided by the suspending or terminating party to the IRB. If the study is prematurely terminated or suspended, the PI will promptly inform the IRB and will provide the reason(s) for the termination or suspension. Circumstances that may warrant termination or suspension include, but are not limited to:

- Determination of unexpected, significant, or unacceptable risk to participants
- Demonstration of efficacy that would warrant stopping
- Insufficient compliance to protocol requirements
- Data that are not sufficiently complete and/or evaluable
- Determination of futility

Study may resume once concerns about safety, protocol compliance, data quality are addressed and satisfy the sponsor, IRB and DSMB.

6 Study Agent (Study drug, device, biologic, vaccine etc.) and/or Procedural Intervention

6.1 Study Agent(s) and Control Description

Mavyret is available in tablet form. The single tablet contains two active agents: glecaprevir (100nmg) and pibrentasvir (40mg).

- No IND is required, as we are not intending to get a new indication for the use of this FDA-

CONFIDENTIAL

approved agent for the treatment of HCV or to change the marketing for Mavyret.

- This investigation does not involve a route of administration, dosing change, or patient population change compared to what is FDA-approved for Mavyret
- This investigation will be conducted in compliance with the NYULMC IRB review and consenting requirements
- This investigation is not intended to promote or commercialize the product Mavyret.

In this particular situation, it is safe to believe that in most of the cases the transplanted lungs are infected with HCV, more likely with a low viral load but still infected, and that the use of Mavyret is for the treatment of Hepatitis C, even if at the time of the transplant there is no evidence of a HCV viremia. We understand this risk and we will have clear communicating with our patients during the acknowledge introduction of this trial (during listing) and also at the time of the consent for the study that we are transplanting an organ with high likelihood of HCV infection. Then the use of this medication is for the intended use of treating HCV infection. The drug is marketed and will be available through the pharmacy.

6.1.1 Acquisition

These agents are FDA approved and will be obtained from the NYU pharmacy via standard procedure for medication ordering.

6.1.2 Formulation, Appearance, Packaging, and Labeling

This is an open label study and the drug will appear as it provided directly from the manufacturer. The tablets are pink, oblong-shaped, film-coated, and debossed with "NXT" on one side. The drug will be packed in the standard manufacturer's packing and all standard and package inserts will be retained.

6.1.3 Product Storage and Stability

Mavyret is dispensed from the manufacturer in a 4-week (monthly) or an 8-week carton. Each weekly carton contains seven daily dose wallets. Each monthly carton contains four weekly cartons. Each 8-week carton contains 2 monthly cartons. Each child resistant daily dose wallet contains three 100 mg/40 mg glecaprevir/pibrentasvir tablets. Storage is at room temperature.

6.1.4 Preparation

The drug is a tablet for oral ingestion, which requires no preparation. For patients with prolonged intubation the medication will be crushed and administered to the patient via nasogastric tube.

6.1.5 Dosing and Administration

The dose will be three tablets taken at one time, once daily with a meal. The standard duration of therapy is 8-weeks. Patients requiring administration via nasogastric tube will have the same frequency of the dosing as oral. When the patient has been extubated and are cleared for oral medications, they will be converted to the oral preparation.

6.1.6 Route of Administration

Administered orally or via nasogastric tube.

6.1.7 Dose Adjustments/Modifications/Delays

No dose adjustments are anticipated. Subjects will be counseled as to the importance of strict adherence to the medication regimen. Subjects will be advised to notify the study team of any missed or delayed doses. If a dose is missed and less than 18 hours have elapsed since the scheduled time, patients will be instructed to take the missed dose with the next meal and resume the regular schedule the following day. If a dose is missed and more than 18 hours have elapsed since the scheduled time, then the patients will be instructed not to take the missed dose, but to resume the regular schedule the next day.

CONFIDENTIAL

6.1.8 Duration of Therapy

The duration of therapy will be 8-weeks.

6.1.9 Tracking of Dose

While in the hospital, nursing staff will give any doses and accountability will be maintained in the electronic medical record. Once outpatient, patients will attend regularly scheduled clinic appointments for routine care following a lung transplant and medication review will occur on each of these visits to ensure that the medication is being taken properly. Laboratory testing for HCV will be performed as described. Clearance of HCV and SVR will serve as clinical evidence that the medication is being taken properly.

6.2 Study Agent Accountability Procedures

For therapy that is initiated during the inpatient hospitalization post-transplant, the NYU Langone pharmacy will dispense the medication and the bedside nurse will give it to the patient. For outpatient therapy, the drug will be distributed to the study subjects together with the standard of care medications they will require after a lung transplant. The drug is supplied in either 4-week or 8-week batches. Completion of the course will leave no remaining doses. The entire supplied product will be used.

7 Study Procedures and Schedule

7.1 Study Procedures/Evaluations

7.1.1 Study Specific Procedures

Note that the medical history and medication history that pertains to candidacy for lung transplantation are considered standard of care procedures and evaluations for lung transplantation, and are not considered here. Patients are not considered candidates for this trial if there is any contraindication to their standard candidacy for a lung transplant. As such, procedures and evaluations specific to participation in this study include:

- Medical history to assess for any history of acute or chronic liver disease, and any prior infection with HCV or HBV (Standard of Care/Per Lung Transplant Protocols)
- Medication history to assess for any potential interacting drugs including (amiodarone, statins, anti-epileptics, hormonal contraceptives, antipsychotics, recreational drugs, immunosuppressant drugs) (Standard of Care/Per Lung Transplant Protocols)
- Physical examination (height, weight, baseline blood pressure, heart rate, oxygen saturation, assess for absence of jaundice/scleral icterus, abdominal examination to assess for absence of hepatosplenomegaly, ascites, abdominal wall varices) (Standard of Care/Per Lung Transplant Protocols)
- Laboratory evaluations. Serum evaluation for HCV and HBV quantitative (PCR) testing. Serum evaluation for HCV and HBV described in detail below.
- A discussion of if the results of any positive blood tests for HCV infection and discussions of response to treatment once treatment has begun.

7.1.2 Standard of Care Study Procedures

Lung transplantation and all associated procedures will be considered standard of care including: the transplant procedure itself and requisite intra-operative procedures and hemodynamic monitoring, post-operative ICU-level care, inpatient hospital unit care, outpatient post-operative care including, standard induction and maintenance immunosuppression, and standard post-transplant anti-infectious prophylaxis (anti-fungal, anti-pneumocystis, and anti-CMV prophylaxis).

CONFIDENTIAL

7.2 Laboratory Procedures/Evaluations

7.2.1 Clinical Laboratory Evaluations

The following tests will be reviewed for patients who are included in the study but will be performed as standard of care for lung transplant recipients:

- **Hematology:** hemoglobin, hematocrit, white blood cells (WBC) with differential count, platelet count
- **Biochemistry:** sodium, potassium, CO₂, BUN, creatinine, total bilirubin, alanine aminotransferase (ALT), aspartate aminotransferase (AST), alkaline phosphatase
- **Coagulation:** INR
- **Pregnancy test,** usually to be done within 24 hours prior to study intervention and results must be available prior to administration of study product.
- **HBV quantitative (Hepatitis B Virus DNA, quantitative Real-Time PCR) testing:** PCR test for detection and quantification of HBV viral load, an indicator of active HBV infection. These tests are performed as standard of care for patients who receive transplanted organs from a donor who is designated "PHS increased infectious risk." By definition, all HCV positive organ donors meet criteria for designation as PHS increased infectious risk.
- **HBV serologic testing (HBsAb, HBsAg, HBcoreAb):** serologic testing to evaluate for the presence of immunity to HBV or the evidence of prior infection with HBV. These tests are performed as standard of care for patients who receive transplanted organs from a donor who is designated "PHS increased infectious risk." By definition, all HCV positive organ donors meet criteria for designation as PHS increased infectious risk.
- **HIV serologic testing (HIV1 and 2 antigen/antibody 4th gen):** serologic testing to evaluate for the presence of HIV infection. These tests are performed as standard of care for patients who receive transplanted organs from a donor who is designated "PHS increased infectious risk." By definition, all HCV positive organ donors meet criteria for designation as PHS increased infectious risk.

The following tests will be performed specifically for purposes of this study:

- **HCV genotyping:** to be performed on all donors in parallel with (not prior to) the transplant, and to be performed for any recipient who develops HCV viremia post-transplant. Donor serum will be sent to Quest Laboratories for this testing (Hepatitis C Viral RNA, Genotype, LiPA[®]). Recipient testing for HCV genotyping will be ordered by standard ordering procedures through Epic as with all other tests.
- **HCV RNA Quantitative (PCR) testing:** PCR test for detection and quantification of HCV viral load
- **HCV serologic testing:** serologic evaluation for the presence of anti-HCV antibodies

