2.4 Potential Risks & Benefits

2.4.1 Known Potential Risks

Risks of treatment failure: HCV mutation can lead to drug resistance and treatment failure. In patients administered Mavyret, the risk of this was 2% or less. For patients with treatment resistant HCV, rescue therapy with alternative agents can result in cure of up to 100% depending upon the genotype. Guidelines for the treatment of resistant HCV strains are published and updated regularly. [16]

Risks of treatment intolerance: Over multiple clinical trials. The overall rate of medication related adverse events leading to permanent discontinuation prior to completion of an 8-week course of therapy was 0.1% [17].

Risk of acute hepatitis C infection: Acute hepatitis C is asymptomatic in 66-75% of patients. The risks of acute HCV leading to fulminant hepatic failure are believed to be very low, however case reports of this do exist [18]. To minimize this already very low risk, we are starting treatment in all the patients at the time of transplant before any viremia is even detected.

Risk of chronic hepatitis C infection: Patients who prove refractory to all therapy including rescue therapy and develop persistent viremia are at risk to develop chronic HCV infection, which has the potential to cause cirrhosis/end-stage liver disease, the potential for the need for liver transplantation and/or death. We expect our treatment failure rate in this study to be 0%, therefore we expect the risk of chronic HCV infection to be 0%. In the event of a treatment failure, the risks of developing chronic HCV must be considered. It is estimated that approximately 15-30% of patients with chronic HCV develop cirrhosis/end-stage liver disease over 20-30 years. [19]. This risk should be compared to the risk of death on the lung transplant waiting list. The reported one-year mortality for a waitlisted patient without a transplant is as high 26.7% [20].

The efficacy of HCV treatment with Mavyret is high (98%). The efficacy of rescue therapies approaches 100%. Even in the event of a treatment failure, the risk of cirrhosis and liver disease secondary to chronic HCV are low. We believe that the survival benefit of receiving an earlier lung transplant, by accepting an organ from a HCV-positive donor, far outweighs the risks of HCV exposure and possible treatment failure.

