8.1.1 Definition of Adverse Events (AE)

An **adverse event** (AE) is any symptom, sign, illness or experience that develops or worsens in severity during the course of the study. Intercurrent illnesses or injuries should be regarded as adverse events.

For the purpose of this protocol an adverse event is any untoward medical occurrence in a clinical study subject associated with procedures required by this protocol in relation to Mavyret treatment.

An AE does not include the following for this study:

- Any medical condition or clinically significant laboratory abnormality with an onset date before the consent form is signed and before day 1 visit is not an AE.
- Any medical condition or clinically significant laboratory abnormality with an onset date after the consent form is signed that is not related to the study medication.

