10.3 Analysis Datasets

Subjects will be entered into a study subject dataset which includes de-identified information. This will include: donor and recipient demographic data, donor HCV RNA quantitative (PCR), serology, and genotyping information, and results of all recipient HCV RNA quantitative (PCR), serologic, and genotyping data obtained throughout the course of the study.

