10.4 Description of Statistical Methods

Since the anticipated study population will be a small size, statistical analyses will be limited to descriptive statistics. For patients who develop post-transplant viremia we will be able to compare our HCV cure rates to those that are expected for patients who receive treatment with these agents for chronic HCV.

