10.4.1 General Approach

The study design will be single arm, open label. Descriptive statistics will include:

- Incidence HCV viremia post-transplant (percentage)
- Time course of exposure to development of clinically detectable viremia in those who develop viremia (median time to viremia with standard deviations)
- Incidence of sustained clearance of HCV (cure) after treatment of viremia (percentage)
- Time course of clearance of viremia after treatment initiation (median time to clearance with standard deviations)
- Incidence of treatment failure/treatment resistant strains of HCV (percentage)
- Characterization of distribution of HCV genotypes in patients who develop viremia (percentages)
Comparison of treatment failure rates to expected treatment failure rates for the treatments used (p value for significance will be set at $p < 0.05$ and two-tailed t-test will be used)

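### Liver tests are reviewed but not listed in the analysis dataset or any planned summary, and the protocol contradicts itself on whether a non-serious HCV-driven rise is recorded as an adverse event

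*Combined protocol and SAP*

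**What the plan says.** **Collection.** Section 7.2.1 introduces a list of routine tests with "The following tests will be reviewed for patients who are included in the study but will be performed as standard of care". The biochemistry line includes "total bilirubin, alanine aminotransferase (ALT), aspartate aminotransferase (AST), alkaline phosphatase", and INR is listed under coagulation. Section 14.1 keeps clinical laboratory data in subject binders, and 14.5 treats standard-of-care testing as outside the study. The schedule of events (section 19) names only HCV tests as laboratory tests.

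**Risk and objective.** Safety is half of the primary objective (3.1). Section 2.4.1 says "The risks of acute HCV leading to fulminant hepatic failure are believed to be very low", adds that case reports exist, and puts the share of acute infections without symptoms at 66-75%.

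**Dataset and analysis.** Section 10.3 says "This will include: donor and recipient demographic data, donor HCV RNA quantitative (PCR), serology, and genotyping information", and then "results of all recipient HCV RNA quantitative (PCR), serologic, and genotyping data obtained throughout the course of the study". Under 10.4, "statistical analyses will be limited to descriptive statistics". The list in 10.4.1 covers viremia, clearance, treatment failure and genotype, and ends with "Comparison of treatment failure rates to expected treatment failure rates for the treatments used". Sections 10.4.2 and 10.4.3 cover SVR, one-year survival and incidence of viremia. Section 10.1 states that there will be no separate SAP.

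**Adverse events.** Section 8.1.1 removes from the AE definition any "clinically significant laboratory abnormality with an onset date after the consent form is signed that is not related to the study medication". Sections 8.2.2, 8.3 and 8.4.1 read differently, as set out under the working.

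**The concern.** Section 4.2.1 justifies SVR as the primary endpoint partly as a way to judge the safety of brief exposure to HCV, and 4.2.2 says the secondary endpoints will allow the risks to be assessed. None of these endpoints measures the liver. SVR and one-year survival could both be 100% whatever happened to liver tests in between. The trial could then conclude that the strategy is safe without having tabulated evidence on a risk that the protocol itself names, although the results are already in each recipient's chart. This does not question SVR as the primary endpoint.

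**Working it through.** **1. Where the liver tests go**

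| Section | Content | Liver tests? |
|---|---|---|
| 7.2.1 | routine tests reviewed | yes |
| 10.3 | demographics; HCV PCR, serology, genotype | not listed |
| 10.4.1 | viremia, clearance, failure, genotype | no |
| 10.4.2-10.4.3 | SVR, survival, incidence of viremia | no |
| 10.4.8 | individual data, chiefly viremia kinetics | not named |

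No row in section 10 contains an AE or SAE summary.

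**2. Whether a non-serious, HCV-driven rise is an AE**

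- 8.1.1: no, if it is not related to study medication.
- 8.2.2: the relationship assessment does not decide what is reported.
- 8.3: a participant's deterioration at any time is an AE. (The sentence follows one on conditions present at screening, so its reach is open to reading.)
- 8.4.1: all AEs go on CRFs, and those judged unrelated go to quarterly DSMB review.

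These cannot all be followed. A rise judged related to Mavyret would be an AE under any of them.

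**3. What happens if the event is serious**

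Section 8.3 documents every SAE whatever its cause, 8.4.2 reports it, and 8.5 halts enrollment if it is attributed to acute HCV. Section 10.4 still plans no table of it.

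**4. Number at risk**

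Section 10.5 gives 20 recipients, about 70% infected, and an estimated 7 treated. The stated 7 does not reproduce: 20 × 0.70 = 14 viremic, leaving 6 not viremic. Seven would need 7/20 = 35% transmission, or 7/0.70 = 10 recipients. That is a separate inconsistency; both values are carried here.

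**5. Infections without symptoms**

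Applying the 66-75% of 2.4.1 (assumed to hold in lung recipients):

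- n = 14: 14 × 0.66 = 9.2 to 14 × 0.75 = 10.5, about 9 to 11.
- n = 7: 7 × 0.66 = 4.6 to 7 × 0.75 = 5.3, about 5.

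In these recipients laboratory tests would be the main evidence of any liver injury.

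**6. What a liver summary could show**

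Exact two-sided 95% upper limit for zero events in n: 1 − 0.025^(1/n).

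- n = 14: 1 − 0.025^(1/14) = 0.232.
- n = 7: 1 − 0.025^(1/7) = 0.410.

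Chance of at least one event at true rate p: 1 − (1 − p)^n. The documents give no rate, so p is an assumed range.

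| p | n = 14 | n = 7 |
|---|---|---|
| 5% | 51% | 30% |
| 10% | 77% | 52% |
| 20% | 96% | 79% |

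A table would probably show an effect that is not rare. A clean table would still leave wide uncertainty, which should be stated.

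**The case against.** The best defence is that safety is watched elsewhere. AEs go on CRFs, the DSMB reviews cumulative safety data quarterly (8.6), and an SAE attributed to acute HCV halts enrollment (8.5). A fragment within 7.2.3 also refers to illness from acute HCV and to documenting AEs and SAEs. Most of section 7.3 is missing from the text available, so liver tests may be scheduled by visit there, and the CRF was not available. All of this stands as evidence of monitoring. None of it creates a summary in section 10.

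Absence from 10.3 is weak evidence on its own. The section says what the dataset will include, not that it holds nothing else, and it also omits vital status and treatment dates, which other planned summaries need. This stands. But no summary in 10.4 calls for liver tests, whereas those other items are implied by the analyses.

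A reader might infer that HCV liver injury goes unrecorded unless it becomes an SAE. The documents do not support this, in either direction. Sections 8.2.2, 8.3 and 8.4.1 offer a route for non-serious events, and becoming an SAE brings reporting and possible halting but no planned summary. Seriousness is not the dividing line.

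A reader might also infer that liver injury is the price of delaying treatment. Sections 2.1 and 19 start treatment once viremia is detected, but 2.4.1 says it starts at transplant, before detection. Under the first reading, PCR is scheduled weekly to POW12, which limits undetected viremia. The documents give no rate of liver injury under either reading.

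Finally, in a 20-patient descriptive pilot a liver table might be called a preference. That would be fair if safety were not half of the primary objective.

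**Conclusion.** The point holds in this form. Liver tests are reviewed but are not listed in the dataset or used in any planned summary. Section 10.4 also has no AE or SAE summary, and the AE passages contradict each other on non-serious HCV-driven rises. The plan as written would therefore support a safety conclusion without a tabulated look at the liver. About 14 recipients are affected on the 70% assumption, or 7 on the stated number treated, and zero events would leave upper limits of 23% or 41%. It rests on section 10 being the whole analysis plan, as 10.1 implies, and does not depend on which start of treatment applies. It should be corrected, but it touches neither the primary endpoint nor the conduct of treatment.

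**What to change.** 1. Add ALT, AST, total bilirubin, alkaline phosphatase and INR to the 10.3 dataset.
2. Add one descriptive output to 10.4.1. For each recipient give the baseline and the peak ALT, AST, total bilirubin and INR, listed with the date of first viremia. Summarise as median and range by viremic status. Give the number above multiples of the upper limit of normal, fixed before analysis, with exact 95% intervals.
3. Use one window for all recipients, for example transplant to POW52. A peak can only rise with longer observation, so ending the window at the SVR sample for viremic recipients alone would favour them. With viremia at POW1 to POW12, 8 weeks of treatment started promptly and about 13 weeks to the SVR sample, that sample falls at roughly POW22 to POW33.
4. Add a table of AEs and SAEs to 10.4.1.
5. Reconcile 8.1.1 with 8.2.2, 8.3 and 8.4.1 on what counts as an AE, and 2.4.1 with 2.1 and section 19 on when treatment starts. Which rule applies is for the study team to decide.

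The cost is CRF fields if they are not already there, two tables and an amendment, with no new blood tests. Limits to state with the results: peaks depend on how often routine samples are drawn and include perioperative changes, and a comparison of about 14 with 6 recipients is descriptive only.
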